6.4.2.12 Immune Response Analyses

Plasma and/or serum cytokine levels will be assayed using enzyme-linked immunosorbant assay (ELISA) methodology. One or more serum biomarkers (eg, MUC-1) or cytokines will be assessed.

6.4.2.13 INXN-1001 Pharmacokinetic Assessment

INXN-1001 PK assessment will occur for subjects enrolled in Part 1 during Cycle 1 of study treatment. Whole blood samples will be collected on Day 1, Day 2, Day 7, and Day 8; as defined in [Table 2A](#), Schedule of Assessments. INXN-1001 levels will also be assessed using the samples drawn for cytokine analysis.

6.4.3 Efficacy Assessments

Appropriate cancer staging procedures should be performed during screening. For the purpose of this clinical trial, the following imaging is expected at screening:

- a. CT of the chest, and CT (or MRI) of the abdomen
- b. MRI (or CT) of the brain if brain metastasis are known or suspected

c. CT or MRI of other anatomical regions as clinically indicated

For each subject, disease sites are to be assessed throughout the study using the same method(s) of assessment used at screening. Chest and abdomen imaging are required for all follow-up imaging time points; images of the brain and other anatomical regions should be acquired on follow-up if positive at screening and as clinically indicated.

Target and non-target lesions should be selected and measured as per mRECIST v1.1 guidelines³⁹ (see [Appendix 4](#)). Lesions that will be/are injected with INXN-2001 and/or biopsied should not be selected as target lesions, but should be assessed as non-target lesions. For each subject, disease sites are to be assessed throughout the study using the same method(s) of assessment used at screening. Tumor response assessments will occur at 12 weeks, 16 weeks, and the Follow-up Tumor Assessment visit (24 weeks) for all subjects, including those who may have experienced a dose delay. Additional tumor response assessments may occur at the discretion of the investigator.

The investigator will evaluate each subject for response to therapy according to mRECIST v1.1 guidelines.

In the setting of this immunotherapy, a progression observed \leq week 12 requires confirmation at week 16 (see [Appendix 4](#) for further details). Subjects without objective evidence of disease progression at the Follow-Up Tumor Assessment visit should continue to have tumor assessments performed at 8-10 week intervals until disease progression has been documented, or an alternate anticancer therapy has been initiated, or up to 1 year, whichever occurs first.

In addition to radiological imaging techniques, photographs of visible cutaneous lesions should also be obtained. Digital photograph(s) with included measuring tape should be taken of all visible injected and non-injected tumors, and of any remaining visible local reactions in or around the injected lesion(s). Important guidelines regarding photographic methodology will be provided in a separate manual.

6.4.4 For Participating Sites: Assessments of Transgene Function, Immunological Activities and Biological Effects (please refer to [Appendix 6](#))

6.4.4.1 Transgene Function

For subjects receiving Ad-RTS-hIL-12, punch biopsies (PBx) or fine-needle aspirates (FNA) of the tumor(s) and/or associated tumor-involved draining lymph nodes will be collected for in vivo assessment of the presence of the adenoviral vector, possible ongoing transgene expression of IL-12, and expression of IL-12-induced downstream genes. Expression of IL-12 and IL-12-induced genes will be evaluated via qRT-PCR, using a panel of primers to known IL-12 regulated genes in breast cancer as well as signaling pathways downstream from IL-12.

For all subjects, FNAs of the tumor(s) and/or associated tumor-involved draining lymph nodes will be collected for immunohistochemistry (IHC).

If a non-injected distal lesion responds to treatment, then an FNA will be obtained to assess the presence of the adenoviral vector and evaluate the mechanism of the response.

6.4.4.2 Immunological Activities

Part of the biopsied tumor(s) will be evaluated by IHC to assess cellular infiltration in the tumor. Cellular infiltration by effector cells, such as T cells and their subsets CD4+, CD8+, and CD56, will be evaluated as well as immune suppressor elements, such as T-regulatory cells (Tregs). Biopsy specimens will also be evaluated for markers of immune activation. Blood will be drawn for assessing cell-mediated immunity, especially frequency of cytotoxic T lymphocytes (CTLs) and Tregs. PBMCs incubated with a pool of breast cancer antigen-derived peptides will be assayed by ELISPOT and/or flow cytometric intracellular staining for relevant cytokines to enumerate the anti-breast cancer CTLs.

6.4.4.3 Other Biological Effects

Tumor biopsies and FNAs will also be assessed for changes in the frequency of apoptotic tumor cells and for other biologic effects of the treatment, such as change in tumor vasculature as a result of induction of IL-12 and other cytokines in the tumor microenvironment.

[REDACTED] An analysis of tumor infiltrates will be performed by IHC with Abs to different immune cell population markers such as CD3, CD4, CD8, CD25, FOX-P3, CD56, etc.

7. ADVERSE EVENTS

7.1 Adverse Event (AE) Definition

An AE is any untoward medical occurrence associated with the use of a drug in humans, whether or not considered drug-related. Any worsening of a pre-existing condition, which is temporally associated with the use of the study drug, is also an AE.

Adverse events include:

- Suspected adverse drug reactions;
- Reactions from study drug overdose, abuse, withdrawal, sensitivity, or toxicity;
- Significant changes or abnormalities when compared to baseline, in signs, symptoms, clinical laboratory results, or physiological testing. This includes any worsening of a pre-existing condition temporally associated with the use of study drug;
- Other untoward medical events, regardless of their relationship to the study drug, such as injury, events that require surgery, accidents, extensions of symptoms, or apparently unrelated illnesses.

The following considerations apply when identifying an AE:

- Anticipated day-to-day fluctuations of pre-existing conditions, including the disease under study, that do not represent a clinically significant exacerbation or worsening need not be considered AEs.
- In the event that a constellation of symptoms results in a confirmed diagnosis, the diagnosis (not the symptoms) should be recorded as the AE term.
- If a diagnosis cannot be established, the symptoms should be recorded as the AE(s).
- If an ongoing symptom has been included in the medical history, an associated severity grade and frequency should also be documented so that a worsening in severity or frequency of a symptom can be readily identified as an AE.
- Progression of disease is not itself an AE; however, the presenting sign or symptom of the disease progression should be documented as an AE (eg, increase in pain).
Exception: If a subject experiences progression of disease that results in death, ‘progression of disease’ may be reported as an SAE if, by medical opinion, the term best describes the cause of death.

7.2 Evaluation of Adverse Events (AEs)

7.2.1 Determination of Seriousness

The investigator will determine the seriousness of an AE based on the following:

7.2.1.1 Serious Adverse Event (SAE)

An AE is considered an SAE if at least 1 of the following conditions applies:

- Death: An AE that results in death during the active study period or within 30 days following study drug administration. In addition, a reported death at any time post-study that is thought to be related to study drug administration;
- Life-threatening adverse event: An AE that places the subject, in the view of the investigator, at immediate risk of death from the event as it occurred (ie, this does not include a reaction that, had it occurred in a more severe form, might have caused death);
- Permanent, persistent, or significant disability: A disability is defined as any substantial disruption of a person’s ability to conduct normal life functions;
- Inpatient hospitalization or prolongation of existing hospitalization: In general, hospitalization refers to admission of a subject into a hospital for at least a 24-hour stay. Hospitalizations for routine blood transfusions, hospitalization for an elective or diagnostic procedure, or surgery for a pre-existing condition that has not worsened, are not considered SAEs. (Emergency room visits that do not result with admission are not considered as SAEs);
- A congenital anomaly/birth defect: A fixed, permanent impairment established at or before birth;

- Important medical event: Events that may not result in death, be life-threatening, or require hospitalization may be considered SAEs when, based upon appropriate medical judgment, they jeopardize the subject and require medical or surgical intervention to prevent a life-threatening situation, hospitalization or death;
- New cancer: Occurrence or diagnosis of a new cancer during the trial is considered an SAE. (This does not pertain to metastasis of current disease);
- Any AE associated with an overdose of the study drug: An overdose of study drug is defined as an occurrence of administered dose exceeding that which is prescribed by the investigator per protocol.

7.2.1.2 Non-Serious Adverse Event

Adverse events that do not fulfill the previous criteria are classified as non-serious AEs.

7.2.2 Determination of Severity

The severity of AEs will be assessed according to the NCI CTCAE, v. 4.03. If the AE is not defined in the NCI CTCAE, v. 4.03, the investigator will determine the severity of an AE based on the following definitions:

- Mild (Grade 1): The AE is noticeable to the subject, but does not interfere with routine activity. The AE does not require discontinuing administration or reducing the dose of the study drug.
- Moderate (Grade 2): The AE interferes with routine activity, but responds to symptomatic therapy or rest. The AE may require reducing the dose, but not discontinuing administration of the study drug.
- Severe (Grade 3): The AE significantly limits the subject's ability to perform routine activities despite symptomatic therapy. In addition, the AE leads to discontinuing administration or reducing the dose of the study drug.
- Life Threatening (Grade 4): The AE requires discontinuing administration of the study drug. The subject is at immediate risk of death.
- Death (Grade 5): The subject dies as a direct result of the complication or condition

Adverse events should be reported using the maximum intensity of the event (eg, if a subject reported nausea lasting 3 days, 1 start date and stop date should be recorded along with the maximum intensity experienced for that event over that 3-day timeframe).

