6.2.5 Retreatment Criteria, Dose Delays and Modifications

Subjects may receive up to 6 cycles of study drug treatment. To receive each repeat treatment cycle, all treatment-related AEs must have resolved to Grade 1 or baseline and the following laboratory criteria must be met:

Hemoglobin \geq 9 g/L	eGFR \geq 60 mL/min/1.73 m ²
Lymphocytes $>$ 700/ mm ³	AST and ALT \leq 2.5 x ULN For subjects with documented liver metastases, ALT and AST \leq 5 \times ULN
Neutrophils \geq 1,500/ mm ³	Total bilirubin $<$ 1.5 x ULN
Platelets \geq 100,000/ mm ³	INR and PTT $<$ 1.5 x ULN

Clinical laboratory tests drawn pre-treatment for analysis on Day 1 of each cycle may be used for determining if the re-treatment criteria have been met, and must be reviewed by the investigator or designee prior to the next cycle of study drug administration. Two treatment delays for recovery to acceptable levels are allowed at weekly intervals up to a maximum of 14 days. In the event that a treatment-related dose delay is necessary for palifosfamide, then the next cycle of study treatment will be administered at 80% of the dose ([Table 3](#)). If an AE is clearly related to 1 study drug and not the other (in combination Treatment Arm C), then dose modification/delay is to occur for the relevant study drug (INXN-1001 and/or palifosfamide). A maximum of two dose reductions, of either INXN-1001 or palifosfamide, will be allowed.

Table 3. Dose Modifications for Palifosfamide-related Toxicity^a

ADVERSE EVENT	PALIFOSFAMIDE
Hematologic	
Platelet count <100 × 10 ⁹ /L	Delay dose of palifosfamide up to 14 days until platelet count ≥ 100 × 10 ⁹ /L, then reduce by 20%.
ANC < 1500/mm ³	Delay dose of palifosfamide up to 14 days until ANC returns to ≥ 1500, then maintain dose when restarted.
Neutropenic fever	Delay dose of palifosfamide up to 14 days until resolved, then reduce by 20%.
Any Grade 4 hematologic toxicity	Delay dose of palifosfamide up to 14 days until Grade ≤ 1 or baseline, then reduce by 20%.
Estimated Glomerular Filtration Rate (eGFR) (Appendix 5)	
≥25% up to <50% decrease from baseline ^b	Hold dose until repeat test is performed. Reduce dose of palifosfamide by 20% if confirmed on repeat test.
≥50% decrease from baseline ²	Hold dose until repeat test is performed. Discontinue palifosfamide if confirmed on repeat test.
Non-hematologic (other than creatinine or urinary electrolyte wasting)	

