7.3 Documenting Adverse Events (AEs)

All AEs (including SAEs) are to be accurately recorded on the Adverse Event page of the subject's electronic CRF from the time the subject signs the informed consent until the Post-Treatment Safety visit. Each event will be assessed for serious criteria, severity, and causality (see "Causality Assessments"). The date of onset, as well as the duration of the event will be recorded. In addition, treatments provided to the subject, actions taken with the study drugs, and the outcome of the AE will also be noted.

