8.4.4 Safety Endpoints

The safety endpoints will include AEs, vital signs, ECG, physical examinations, laboratory data, and concomitant medications. All AEs will be coded according to Medical Dictionary

for Regulatory Activities (MedDRA®, version 13.0 or later). Concomitant medications will be coded using the World Health Organization Drug Dictionary, September 2006 or later.

The incidence, onset timing, duration, severity, relationship, and outcome will be listed for each AE. All treatment-emergent AEs (TEAEs) occurring on-study will be analyzed by treatment group and listed in by-subject data listings. Events that are considered related to treatment (possibly related or related) will also be tabulated.

Treatment-emergent AEs will be tabulated overall and by subject. ‘Treatment-emergent’ is defined as any AE that occurs during or after administration of the first dose of study drug through the Post-Treatment Safety Assessment visit (28 days after last dose of study drug); any event after the first dose of study drug that is considered study drug-related regardless of the start date of the event; or any event that is present at baseline that worsens in intensity or is subsequently considered to be drug related by the investigator. Serious TEAEs and related TEAEs will be summarized in a similar fashion. AEs to be presented will include TEAEs, treatment-emergent SAEs, and treatment-emergent related AEs, as well as the severity of the events. Timing relative to study treatment administration will also be presented. Treatment-related SAEs will also be summarized by treatment group and presented on a case-by-case basis in listings and narratives.

Dosing and study drug tolerability will also be assessed.

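### For adverse events not defined in CTCAE v4.03, the fallback severity scale in Protocol Section 7.2.2 mixes clinical severity with action taken on study drug, so some limiting events fit no grade

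*Protocol*

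**What the plan says.** Section 7.2.2 names the main scale first: "The severity of AEs will be assessed according to the NCI CTCAE, v. 4.03". It then limits its own definitions to the remainder: "If the AE is not defined in the NCI CTCAE, v. 4.03, the investigator will determine the severity of an AE" from the five definitions that follow.

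In those definitions, Grades 1 to 4 each carry a clinical description and a sentence about study drug. For Grade 3 the clinical part is "The AE significantly limits the subject's ability to perform routine activities despite symptomatic therapy", followed by "In addition, the AE leads to discontinuing administration or reducing the dose of the study drug". For Grade 4 the drug sentence is "The AE requires discontinuing administration of the study drug".

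Other sections bear on this:

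- Section 6.2.5 makes treatment depend on grade. For each repeat cycle, "all treatment-related AEs must have resolved to Grade 1 or baseline". The non-hematologic rows of Table 3 also act on Grade 3 and Grade 4 events.
- Section 7.3 collects drug action as its own item: "actions taken with the study drugs, and the outcome of the AE will also be noted".
- The Synopsis lists safety and tolerability as a primary endpoint, and Section 8.4.4 includes severity in the adverse event presentations.

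**The concern.** A severity grade should describe the event. What the investigator did with the drug is a separate fact, and it depends on the arm, the cycle, the investigator and whether any dose remains to change. When that action is part of the definition, two subjects with the same clinical event can receive different grades because one had a dose reduced and the other did not. The grade may also be undefined.

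At stake is the consistency of any severity summary that includes fallback-graded events. The Safety Review Committee sees such summaries after 6 subjects in Arm A and 3 in Arm C, and they also feed the final safety tables.

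**Working it through.** The plan states no figure to reproduce and no rate to recompute. The check is to set the definitions side by side and pass cases through them.

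**Fallback scale, Section 7.2.2 (paraphrased)**

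| Grade | Clinical part | Drug-action part |
|---|---|---|
| 1 | Noticed, routine undisturbed | No stop or reduction needed |
| 2 | Disturbs routine, but treatment or rest helps | Reduction possible, stop excluded |
| 3 | Marked limitation in spite of treatment | A stop or reduction has followed |
| 4 | Immediate risk of death | Event calls for a stop |
| 5 | Death | None |

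**Cases, all for an event outside CTCAE v4.03**

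| Case | Result as worded |
|---|---|
| A. Limiting despite treatment, dose reduced | Grade 3 |
| B. Same event, no change to drug | Not 1 (disturbs routine), not 2 (treatment does not help), not 3 (no action), not 4 (no immediate risk of death): no grade |
| C. Same event, next dose delayed only | As B: a delay is neither a stop nor a reduction |
| D. Same event, after consent but before first dose | As B: no dose has been given that could be reduced or stopped |
| E. Same event, after the last dose | As B: no dose is left to change |
| F. Mild event that requires a reduction | Clinically 1, but excluded from 1 by the action part |
| G. Event that responds to treatment but requires a stop | Clinically 2, but excluded from 2; not 3, because treatment helps |

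**Can cases C to E arise under the protocol?**

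- C: Section 6.2.5 allows delays of up to 14 days. For INXN-1001 it permits reductions but attaches none to a delay. For palifosfamide a treatment-related delay generally brings the next cycle to 80% of the dose, although the ANC row of Table 3 keeps the dose unchanged. Delay without reduction is therefore mainly an INXN-1001 situation.
- D: Section 7.3 records adverse events from the signing of consent.
- E: Section 8.4.4 counts events as treatment-emergent up to the safety visit 28 days after the last dose.

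**Direction.** Cases B to E remove events from Grade 3. In cases F and G, an investigator who must enter some grade may well choose the next one up. The scale can therefore misplace events either way.

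**Circularity.** Table 3 prescribes a 20% palifosfamide reduction, after delay, for certain Grade 3 non-hematologic events. Under Section 7.2.2 a fallback event is not Grade 3 until a stop or reduction has followed. Each section waits on the other.

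**Grade 4.** The fallback definition ties Grade 4 to stopping the drug. The paragraph after Table 3 in Section 6.2.5 allows re-exposure, case by case, after a treatment-related Grade 4 event. These two passages must be reconciled.

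**Does the SAP settle it?** No. The SAP supplied describes a single-arm, single-center Phase Ib/II study. Its Section 9.2 tabulates events by severity without defining a fallback scale.

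**The case against.** The strongest objection is scope. CTCAE v4.03 is the scale for all events it defines, Section 4.1.1.1 repeats this for the safety assessment, and Section 6.2.6 applies it expressly to injection site reactions. A reader might infer from the Grade 3 wording that no severe event in this trial can be Grade 3 without a dose change. The documents do not support that: for any CTCAE-defined event the wording does not apply. This part of the objection stands in full, and the point is confined to the fallback scale.

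Nor do the documents show that the primary safety tables understate severity. They do not say how many events will fall outside CTCAE, and the direction can go either way. That also stands.

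Two mitigations are fair. Life-threatening, disabling or hospitalizing events are captured as serious under Section 7.2.1.1 whatever was done with the drug. Action taken is also recorded separately, so fallback-graded events can be reviewed against it.

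Neither mitigation closes the gap. Serious-event capture does not assign a grade, and a separate action field does not tell the investigator what to enter in case B. This is a stated rule that gives no answer or an inconsistent one, rather than a detail left to a manual.

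**Conclusion.** The point holds as a minor definitional flaw. As worded, the fallback scale gives no grade to a limiting, treatment-resistant, non-life-threatening event that leads to no stop or reduction, and it can grade identical events differently. It is also circular with Section 6.2.5. The size is unknown: it depends on the number of events outside CTCAE v4.03, which may be small or nil, and the net direction of misgrading is unknown. The conclusion rests on reading the Grade 3 definition literally, as two conditions that must both be met.

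Four further inferences are tempting but not supported.

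- **Arm A is affected most, because Table 3 covers only palifosfamide.** Discontinuation also satisfies Grade 3 and is open to both arms, and Section 6.2.5 allows INXN-1001 reductions.
- **Grade 4 cannot be met after the last dose.** Its wording can be read as what the event demands, which can still be judged when no dose remains. The gap is firm only for Grade 3, which describes an action that followed.
- **The effect can be sized from follow-up time or run-in numbers.** For a six-cycle completer without delays, the last INXN-1001 dose falls on day 5 × 21 + 7 = 112 and follow-up ends on day 112 + 28 = 140, so 28/140 = 20% of days follow the last dose. That is a share of days, not of events or grades. One subject in 3 or in 6 is 33 or 17 percentage points, but this presupposes a misgraded event, and the protocol states no Grade 3 rate that triggers a decision.
- **Recording only maximum intensity misdates severe events.** The Section 7.2.2 example is a three-day episode. Section 8.4.4 lists onset timing and says "Timing relative to study treatment administration will also be presented", but does not promise the date of worst grade. A dated grade history is a data-collection preference and does not carry this point.

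**What to change.** In Section 7.2.2, delete the dose-action sentence from each of fallback Grades 1 to 4 and define the grades by clinical effect alone. Keep action taken as the separate item already recorded under Section 7.3. Leave the dosing rules in Section 6.2.5 as they are. If any deleted sentence was meant as a treatment rule, the sponsor should say so and reconcile it with Section 6.2.5, in particular the Grade 4 sentence with the re-exposure paragraph after Table 3.

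The cost is a wording change to four definitions. No data are lost, no new form field is needed, and grading of CTCAE-defined events is unaffected.
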